PROTOCOL TITLE: Gabapentin for pain control after osmotic dilator insertion and prior to D&E procedure: a randomized controlled trial

1) Protocol Title

Title: Gabapentin for pain control after osmotic dilator insertion and prior to D&E procedure: a randomized controlled trial

Protocol Version Date: 01/11/2018

2) Objectives

Pain management in the context of abortion is a topic that is both challenging and necessary to research. The Society of Family Planning (SFP 2014) lists it as a top research priority. Most research to date has focused on pain during the abortion procedure. One area that remains under investigated is women's pain experience during the time osmotic dilators are in the cervix prior to the dilation and evacuation procedure. As a result, management of pain during this time period varies greatly and is largely based on anecdotal experience. Adjunctive pain management with non-narcotic medications such as gabapentin may have a place during this time. Gabapentin is unique in that it is both well tolerated with minimal contraindications and low cost with 600 mg doses as low as \$0.24. Additionally, widespread dissemination of cell phones and text messaging now gives us the opportunity to communicate with women about their dilator-related pain experience in real-time, potentially improving data quality.

We have planned a randomized, controlled trial of repeated doses of gabapentin compared to placebo for pain management during the time after dilator insertion and prior to D&E the subsequent day. Participants will receive gabapentin 600 mg or placebo prior to dilator insertion. Pain scores will be measured via numeric rating scale (NRS) at baseline and 5 minutes after insertion while the participant is in clinic. Additional pain scores as well as side effect and additional analgesic use will be obtained by text message while the patient is at home at 2 hours, 4 hours, and 8 hours after time of dilator insertion. Final pain score, side effect, and analgesic use assessment will occur upon presentation to the pre-operative area for D&E. We hypothesize that women who receive gabapentin beginning at the time of dilator placement for a D&E procedure will report a smaller increase in pain from baseline at 8 hours after dilator placement compared to women receiving placebo.

3) Background

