3. Participant will be asked to provide pain level on 11-point (0-10) NRS immediately before study drug ingestion as the baseline pain score. Baseline symptoms (sedation and dizziness) will also be recorded.
4. Women will ingest the assigned gabapentin 600 mg or placebo
 - a. Stratified block randomization will occur to achieve even distribution of women based on vaginal parity (no prior vaginal delivery versus one or more prior vaginal deliveries). This strategy will ensure similar numbers of women with vaginal parity between gabapentin and placebo groups as this may be an important factor influencing pain with dilators in general.
 - b. A UC Davis Investigational Drug Services (IDS) pharmacist will use computer-generated randomization to place active or placebo treatment in two groups of sequentially numbered vials (to account for block randomization based on parity)
5. The physician will proceed with dilator insertion via our existing standardized method (including standard cervical anesthesia with 1% xylocaine 20 mL, standard number of dilators based on gestational age). Number of dilators and any pharmacologic means of cervical preparation are already reported in a standardized template and will be available for chart review.
6. Post-dilator pain will be assessed via NRS at five minutes after dilator insertion. Additional symptoms (sedation and dizziness) will be recorded.
7. Women will be discharged home with:
 - a. One additional study medication (Gabapentin 600 mg or placebo) to take at home 8 hours after the initial dose. This medication will be labeled by the IDS and completed by administering physician.
 - b. Standard prescriptions for acetaminophen 300 mg/codeine 30 mg and ibuprofen 800 mg to take as needed.
 - c. A reminder form that includes 24-hour research contact information, the times when they can expect text messages, a reminder to take the home dose of their assigned study medication at 8 hours after dilator insertion (exact time will be written out) and a reminder to bring the empty study medication bottle with them when they present for their procedure the next day.
 - d. Recommendation that they have a ride to and from abortion procedure the subsequent day.
8. Participants will be sent a baseline text message from the study phone prior to leaving the clinic. Participants will be encouraged to enable privacy features on their personal phone. Examples of security features will be reviewed and included in the consent.

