PROTOCOL TITLE: Gabapentin for pain control after osmotic dilator insertion and prior to D&E procedure: a randomized controlled trial

8) Data and/or Specimen Management and Confidentiality

Sample size calculation

For the purpose of calculating sample size, there is no existing data that truly mirrors the objective of this study (context of pain, use of NRS, and use of change in pain score from baseline). The closest approximation is the mean immediate post-dilator insertion pain score of 5.2 (SD 1.2) via NRS from Borgatta, et al (2012). However, when using this data point and a commonly cited clinically significant decrease in NRS pain score of 2 points, computation with SAS 9.1 (factoring in power at 80% ($\alpha=0.05$), normal distribution) yielded a small sample size of only 12 women per group. [27-33] Based on the block randomization there are four groups for a total of 48 women. To account for up to 20% of subjects not responding to text messaging for the primary outcome the sample size estimate will increase to 58 total women. To ensure we gather sufficient data to truly outline pain experience during the dilator-procedure interval, we will more than double the sample size to recruit 121 women. We will stratify these 121 women by presence or absence of prior vaginal parity. Ensuring similar distribution of vaginal parity between the gabapentin and placebo groups is important as vaginal parity may affect pain with osmotic dilators.

Statistical Analysis

We will use non-parametric testing to assess the primary outcome variable because we do not expect normal distribution of the data. Chi square analysis and fisher exact tests will be used to compare demographics and dichotomous variables as appropriate. I plan to describe the pain course for the total study cohort using means and medians as appropriate.

Data Management

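### The primary analysis text does not use the randomised parity strata and plans no between-arm difference with a confidence interval

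*Combined protocol and SAP*

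**What the plan says.** **Analysis.** The Statistical Analysis text in Section 8 has three sentences. The primary outcome gets one: "We will use non-parametric testing to assess the primary outcome variable because we do not expect normal distribution of the data". The second covers chi-square and Fisher tests for demographics and dichotomous variables. The third reads "I plan to describe the pain course for the total study cohort using means and medians as appropriate". No test is named for the primary outcome, parity is not mentioned, and no difference between arms or confidence interval is planned.

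**Outcome.** Section 8 does not define the primary outcome variable, and Section 6 uses the term primary endpoint for enrolment of 121 women. The outcome has to be inferred from the hypothesis in Section 2, that women given gabapentin will "report a smaller increase in pain from baseline at 8 hours after dilator placement compared to women receiving placebo".

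**Strata.** Section 7, item 4a: "Stratified block randomization will occur to achieve even distribution of women based on vaginal parity", on the ground that "this may be an important factor influencing pain with dilators in general".

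**Sizing.** The sample-size text in Section 8 takes "a commonly cited clinically significant decrease in NRS pain score of 2 points", with an SD of 1.2 from a single post-insertion score in a cited study. This "yielded a small sample size of only 12 women per group". The same paragraph says that "there is no existing data that truly mirrors the objective of this study". The total then goes from 48 to 58 for non-response and is raised to 121.

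**The concern.** Two things that the design treats as important do not reach the analysis.

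- **Parity.** It is considered likely enough to influence pain to stratify the randomisation on it, and it multiplies the group size in the sample-size text. If it does influence the change in pain, a rank test that ignores it leaves that variation in the comparison.
- **The 2-point difference.** It is the starting value of the formal calculation and is described as clinically significant. A rank test alone returns a p-value and says nothing in NRS points. Pain scores are to be summarised only for the cohort as a whole, so the plan does not commit to showing even the two arms' scores side by side.

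Several tests fit the sentence as written, so the choice between them could be made after the data are seen. At stake are some efficiency and, more importantly, whether the result can be read against the difference that the trial set out to look for.

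**Working it through.** **1. Where the 2 points enter.** 12 per group × 4 arm-by-parity cells = 48. 48 × 1.2 = 57.6, or 58. Twice 58 is 116, so 121 is indeed more than double. The 2-point difference therefore leads to 12, 48 and 58; 121 is a discretionary increase. How the 12 was obtained is a separate matter and is not used here.

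**2. Evaluable women.** 121 × (1 − 0.20) = 96.8. Taking 96 with equal allocation (assumed; the ratio is not stated) gives 48 per arm.

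**3. Precision.** The half-width of a two-sided 95% CI for the difference in mean change is 1.96 × SD × √(2/48), with √(2/48) = 0.2041. A rank-based interval is approximated with the t quantile on 94 degrees of freedom, divided by √0.955. The SD of the change is not in the documents, so only 1.2 is the plan's figure, and that is the SD of a single score.

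| SD of change | Mean difference, half-width | Rank-based, approximate |
|---|---|---|
| 1.2 (plan) | 0.48 | 0.50 |
| 1.7 (assumed) | 0.68 | 0.71 |
| 2.5 (assumed) | 1.00 | 1.04 |
| 3.0 (assumed) | 1.20 | 1.24 |

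**4. What the interval adds.**

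- Observed reduction 1.0, SD 1.2: 1.0 ± 0.48 = 0.52 to 1.48. Significant, and 2 points is excluded.
- Observed 1.5, SD 2.5: 1.5 ± 1.00 = 0.50 to 2.50. Significant, but 2 points is not excluded.
- Observed 1.0, SD 3.0: 1.0 ± 1.20 = −0.20 to 2.20. Not significant, and 2 points is not excluded.

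A p-value gives the first two the same label. In simulation (set-up in step 5) with an assumed true effect of 1 point, a van Elteren test gave p<0.05 in about 97% of trials at SD 1.2 and 78% at SD 1.7. In about 94% and 60% of all trials, respectively, the result was significant while the CI lay wholly below 2 points. At SD 2.5 and 3.0 significance fell to about 46% and 34%, and the combination to about 8% and under 1%.

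**5. What the strata are worth.** Simulation with 10,000 trials per cell, 96 women, 1:1 within two parity strata, and per-arm splits of 24/24 or 14/34. Assumed: baseline mean 1 and SD 1, placebo 8-hour mean 5.2, normal errors, scores rounded and clipped to 0–10, SD of change 1.2 to 3.0 before clipping. The parity shift is also assumed, since the documents give none.

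Type I error at nominal 5%:

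| Parity shift | Unstratified rank test |
|---|---|
| 0 | 4.7–5.2% |
| 1 point | 3.3–5.0% |
| 2 points | 1.0–4.3% |

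The van Elteren test stayed at 4.2–5.4% throughout.

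Power of van Elteren minus unstratified, in percentage points:

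| True effect | No shift | 1-point shift | 2-point shift |
|---|---|---|---|
| 1.4 | −0.8 to 0 | 0 to +1.0 | +0.1 to +4.9 |
| 1.0 | −0.4 to 0 | +0.5 to +2.1 | +2.9 to +10.7 |

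At the plan's 2 points the gap is −0.3 to +1.8 over all shifts, and both tests have at least 99.9% power at SD 1.2 and 1.7. At 1.4 points and SD 2.5, power is 69–75% unstratified and 74–75% stratified.

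Clipping shrinks the two larger SDs to 2.3–2.4 and 2.6–2.7. The matching half-widths are 1.96 × 0.2041 × SD = 0.92–0.96 and 1.04–1.08, so at those SDs the simulated percentages and the table in step 3 are not on quite the same scale.

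**6. Does a mean-difference CI fit beside a rank test?** In 2,000 trials per cell with a 1-point parity shift, coverage of the parity-weighted mean difference with unequal-variance standard errors was 94.1–95.9%. Test and CI agreed on excluding zero in 96.7–100% of trials at a 2-point effect. At 1 point they agreed in 94.6–99.1% with normal errors and 81.3–98.9% with deliberately extreme exponential errors.

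**The case against.** The strongest reply is that nothing here is wrong as written. A stratified rank test is also non-parametric, so the text does not exclude one. An unstratified test would be valid, and item 4a gives balance between arms as the purpose of stratifying, which the randomisation delivers by itself. The documents only say that parity may matter. The larger gains need an assumed parity shift as big as the 2-point effect. All of this stands, and it makes the strata the lesser part of the point.

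It is also fair that a CI for means sits awkwardly beside a rank test when skew is expected. That is a reason to say in advance which of the two decides significance, or to use a rank-based interval. It is not a reason to plan no interval.

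A reader might infer more than the documents support:

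- *That ignoring parity inflates false positives.* The error goes the other way: the unstratified test becomes conservative.
- *That the plan contradicts itself.* It leaves a gap that either kind of test could fill.
- *That the final 121 rests on 2 points.* Only 12, 48 and 58 do. Section 8 justifies the increase by a wish to describe the pain experience adequately.
- *That the four groups in the sizing mean separate comparisons within parity strata.* The hypothesis compares gabapentin with placebo overall, and no within-stratum comparison is planned. If one was intended, the protocol should say so.

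**Conclusion.** The point holds as an inexpensive improvement that should be made, not as a fault that invalidates the trial.

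The main loss is interpretive. Without a between-arm estimate and CI, the result cannot be read against 2 points, although about 48 evaluable women per arm would give a half-width of roughly 0.5 points at SD 1.2 and 1.0–1.2 at SDs of 2.5–3.0.

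The loss from leaving out parity is smaller and conditional. It is nil if parity has no effect on the change in pain, and not meaningful at the plan's own 2 points and SD 1.2. With a 2-point parity shift the type I error is about 1–4%, and power falls by up to about 5 percentage points at a 1.4-point effect, or about 11 at 1 point. Stratifying when parity has no effect costs under 1 percentage point.

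These figures rest on 20% non-response, equal allocation, a two-sided 5% level (sidedness is not stated), assumed change SDs above 1.2, assumed parity shifts, and 8-hour change from baseline as the primary outcome, which is inferred from Section 2.

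**What to change.** Add a short, dated text to the Statistical Analysis part of Section 8 before allocation is unblinded:

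1. Define the primary outcome as change in NRS from baseline to 8 hours, and name the primary test: van Elteren (rank-sum stratified by vaginal parity), with its significance level and sidedness.
2. Name one parity-stratified between-arm difference in NRS points with a 95% CI, to be read against 2 points. Either a stratified Hodges-Lehmann shift or a parity-weighted mean difference with unequal-variance standard errors would do. The first sits closer to the test; the second is a difference in mean NRS points. Choose one in advance.
3. State that the test decides significance and the CI describes size, since the two can disagree when data are skewed.
4. Summarise the pain course by arm as well as for the total cohort.

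The cost is a few sentences and a few lines of code. Parity, baseline NRS and 8-hour NRS are already collected, and the sample size does not change. Timing is the constraint: this version is dated 01/11/2018 and Section 5 expects the primary analysis by March 2018. The pharmacy service holds the randomisation log and allocation is to stay concealed, so a text dated before unblinding would be credible.

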Based on our current volume, we estimate that we will complete enrollment of 121 women in 12 months (goal of February 2017 – January 2018). Between August 2015 and June 2016, the clinical Family Planning fellow completed 228 D&E from 15 weeks 0 days to 23 weeks 6 days gestational age (on date of procedure) at the UC Davis Medical Center. Completion of the primary analysis will occur by March 2018.

6) Study Endpoints

The primary study endpoint is enrollment of 121 total participants. The study will be reviewed at least monthly to monitor for adverse events that would indicate safety issues and thus a safety-related endpoint. Adverse events will include both

PROTOCOL TITLE: Gabapentin for pain control after osmotic dilator insertion and prior to D&E procedure: a randomized controlled trial

medical concerns and patient privacy concerns given text message contact at home.

7) Procedures Involved

Recruitment will occur in the Division of Family Planning pre-operative clinic held once to twice weekly in the Lawrence J. Ellison Ambulatory Care Center of the UC Davis Department of Obstetrics and Gynecology. This clinic is specifically for patients seeking abortion procedures. Family Planning physicians and/or research assistants will obtain informed consent from eligible women that opt to participate (all family planning attendings and fellows will be trained as study personnel). An institutional HIPAA Authorization form will also be obtained to allow access to participant's medical record for information related to the study. Study information will include demographic traits and information from dilator placement.

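### Does the plan need a named between-arm comparison of as-needed pain pills taken before the 8-hour score?

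*Combined protocol and SAP*

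**What the plan says.** The hypothesis in section 2 (Objectives) is a smaller rise in NRS pain from baseline to 8 hours on gabapentin than on placebo. The same section says that "additional analgesic use will be obtained by text message while the patient is at home". Section 7 gives every participant prescriptions for acetaminophen/codeine and ibuprofen for use as needed, and states that usual care is unchanged. The text messages at 2, 4 and 8 hours ask for the number of pills of each drug since the last text. Use after 8 hours is asked at pre-operative admission.

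Section 8 (Statistical Analysis) has three sentences. For the primary outcome: "We will use non-parametric testing to assess the primary outcome variable because we do not expect normal distribution of the data". For other variables: "Chi square analysis and fisher exact tests will be used to compare demographics and dichotomous variables as appropriate". For description: "I plan to describe the pain course for the total study cohort using means and medians as appropriate". Section 6 adds no analgesic endpoint; it says "The primary study endpoint is enrollment of 121 total participants" and otherwise deals with safety. The sample size text in section 8 uses "a commonly cited clinically significant decrease in NRS pain score of 2 points" and enlarges the calculated number "To account for up to 20% of subjects not responding to text messaging for the primary outcome".

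**The concern.** Pills taken before the 8-hour text can lower the 8-hour score. If women on placebo hurt more and so take more, the arms move closer together on the primary outcome. A reader who sees only the pain difference might set it against 2 points and judge gabapentin too weak, when part of its benefit appeared as fewer pills.

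The tests named for secondary data suit yes/no variables. Any use of a drug fits them, but number of pills does not. If nearly every woman takes at least one pill, a yes/no comparison says little about quantity. With two drugs, several time windows and two codings available, a comparison chosen after unblinding could also be picked for its result. The version is dated 01/11/2018, and section 5 says "Completion of the primary analysis will occur by March 2018", so there was little time to specify one.

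**Working it through.** **Plan figures.** The allowance for non-response reproduces as 48 × 1.2 = 57.6, stated as 58. The 12 per group does not follow from its stated inputs: 2 × (1.96 + 0.84)² × 1.2² / 2² = 5.6, so 6 per group. That is a separate matter, and nothing below uses the 12. Applying 20% non-response to the planned enrolment gives 121 × 0.8 = 96.8, about 48 per arm with an 8-hour score (1:1 allocation assumed).

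**Assumptions.** The documents give no pill-use rate, no arm difference and no effect per pill. The ranges assumed are: difference without pills, 2 points; placebo takes 0.5 to 0.8 more pills; each pill lowers the score by 0.5 to 1 point; SD from 1.2 (the plan's) to 3.0.

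**Step 1: narrowing of the pain difference.** Observed difference = 2 − (extra pills × effect per pill).
- Least: 2 − 0.5 × 0.5 = 1.75.
- Most: 2 − 0.8 × 1 = 1.2.

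A simulation in which pill use rises with pain gives 1.22 to 1.74. This is nearly all arithmetic on the assumptions.

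**Step 2: effect on the primary test.** Power ≈ Φ(difference / (SD × √(2/48)) − 1.96). For a difference of 1.2:

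| SD | Power |
|---|---|
| 1.2 | 99.8% |
| 2.5 | 65% |
| 3.0 | 50% |

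The formula holds the SD fixed. In the simulation the women in most pain take the most pills, which also narrows the spread of scores, and the pain test rejects in 75% to 100% of trials.

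**Step 3: what a named comparison of quantity would show.** The texts ask about each drug separately, so the natural comparison is per drug. In the same model, with pain-driven pills split evenly between the drugs (a further assumption), a parity-stratified rank test (van Elteren) has these chances of detecting the imbalance:

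| Comparison | Women per arm | Power |
|---|---|---|
| Both drugs pooled into one count | 48 | 47–82% |
| Each drug separately | 48 | about 28–58% |
| Each drug separately | 31 | about 20–40% |

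The last row matters because a total to 8 hours needs all three replies. If 20% miss each one independently (assumed), 0.8³ × 121 = 62 women have complete counts, 31 per arm.

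**Step 4: what the yes/no tests already show.**
- Any use of either drug, no routine first pill (69–85% v 51–66%): Fisher's test detects the imbalance in 35–50% of trials.
- Any use of either drug, first pill near-routine (97–99% v 95–97%): under 1%.
- Any use of acetaminophen/codeine alone, when the routine first pill is ibuprofen (assumed, even split): about 21–37%. This comparison is already within the plan's wording.

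**Step 5: choice after unblinding.** With no true difference, 16 possible comparisons (2 drugs × any use or count × 4 windows) give at least one p < 0.05 in 26–30% of simulated trials, against 9–10% for two named tests. The plan lists none of the 16 and makes no claim about analgesic use.

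**The case for a change.** The strongest case for a change is that the data are already being collected, two sentences would suffice, and prespecification cannot be recovered once allocation is known. The wording about chi-square and Fisher tests does not reach quantity. When the share of users is equal, a yes/no test is blind to it: with 80% users in both arms and 2 v 3 pills per user, it rejects at its 5% level while a count test rejects in 65% of simulated trials.

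Much of this stands. No between-arm comparison of quantity is named, counts carry more information than any use, and naming one in advance is good practice.

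It does not show that the plan goes wrong. The 2 points is a sample-size input; the hypothesis asks only for a smaller increase in pain, so no success rule turns on 2 points. Usual as-needed care continues unchanged, so the planned contrast is pain on top of that care. Calling the no-pill difference the true effect replaces that question with another. Pill use also follows randomisation, so comparing counts helps interpretation but does not correct the primary result. A per-drug test with the power in Step 3 could itself mislead if a non-significant result were read as equal pill use.

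**Conclusion.** No change follows. Section 8 omits a comparison that a competent analyst would supply: pills of each drug by arm, set beside the pain result. It prescribes nothing incorrect for these data. The primary comparison is valid with or without that table, and the counts are collected either way.

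The possible harm is a misreading of effect size, and it is hypothetical. It needs pill use to differ by arm, which the documents do not establish; the lower narcotic use they cite comes largely from abdominal hysterectomy, which section 3 says is not a good proxy. It also needs a reader to treat 2 points as a threshold, which the plan does not do. If both held, the assumed ranges would turn 2 points into about 1.2 to 1.75, with the pain test still rejecting in 75% to 100% of simulated trials at 48 per arm. Formal per-drug tests would add little certainty, at about 28% to 58% power with 48 per arm and 20% to 40% with 31. All these figures rest on assumed pill use, an assumed effect per pill and, for the per-drug tests, an even split between drugs.

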The current standard of care at our institution is for women to present for pre-operative evaluation and osmotic dilator placement on the day prior to scheduled D&E. Cervical anesthesia with Xylocaine 1% 20 mL is standardly administered immediately prior to dilator insertion. All providers follow standard guidelines on the number of dilators to place based on gestational age. Xylocaine is the cervical anesthetic standardly used at our institution as well as in other reported pain studies. [20-23] Although bupivacaine has a longer duration of action than xylocaine (2-4 hours and 1-2 hours, respectively), the increased duration does not cover the entire osmotic dilator experience. [24] Additionally, bupivacaine is not commonly used in cervical anesthesia-related abortion literature or clinical practice, limiting generalizability. Only Dilapan-S® hygroscopic cervical dilators are used in our practice. Misoprostol is not used in conjunction with dilators. Mifepristone is only used in the context of suboptimal dilator placement or gestational age of 22 weeks or more. After dilator placement, women standardly receive prescriptions for acetaminophen 300 mg/codeine 30 mg and ibuprofen 800 mg which can be used as needed for pain management during the time between dilator placement and D&E. At UC Davis Medical Center (UCDMC), D&E procedures are completed in the main operating rooms on the day following dilator placement with the aid of deep sedation. **There will be no deviation from the above standard practice for participants in this study.**

Study methodology for this randomized double-blind placebo-controlled trial will proceed as follows:

1. Eligible women at 15 weeks 0 days – 23 weeks 5 days gestational age at time of preoperative appointment will be approached regarding the study prior to dilator placement. Consent will be obtained.
2. Relevant baseline demographics (age, race, ethnicity, education level, gravidity, detailed parity, reported history of anxiety, depression, drug abuse, chronic pain, recent narcotic pain medication use, and reason for pregnancy termination) will be collected. These are standard questions asked of **all** patients during their preoperative abortion evaluation.

PROTOCOL TITLE: Gabapentin for pain control after osmotic dilator insertion and prior to D&E procedure: a randomized controlled trial

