The FDA label for gabapentin lists adverse events reported by studies investigating the drug for management of either epilepsy or postherpetic neuralgia. Both FDA approved indications for gabapentin use a wide range of drug dosing and a significantly longer duration compared to this study. Studies investigating gabapentin for peri-procedure analgesia are powered to detect their primary outcome of pain reduction. Those studies reporting side effects ask about sedation and dizziness most commonly. [34] Gynecologic studies, typically in the context of abdominal hysterectomy, report no statistically significant increase in sedation or dizziness compared to placebo. [13-14] Both studies started with initial doses of gabapentin 1200 mg, which is twice the dosing of this study.[13-14] Dierking et al continued gabapentin dosing for a total of 3000 mg over 24 hours (year). While

PROTOCOL TITLE: Gabapentin for pain control after osmotic dilator insertion and prior to D&E procedure: a randomized controlled trial

participants may be able to understand the FDA risk stratification, delineating frequent, infrequent, and rare adverse events, the risks in the label do not accurately simulate the clinical context of this study.

To minimize risks, the dose of Gabapentin used in this study is comparable to that of prior peri-procedure studies and the same as an ongoing randomized controlled trial through the family planning division at Emory University that is investigating Gabapentin 600 mg versus placebo for pain control during first trimester aspiration abortion. [25] Out of caution, participants will be required to have a ride home from the clinic as criteria for study eligibility so they aren't driving after study medication dosing. Frequency of reported side effects will be closely monitored, as well as any AE or SAEs, per Section 11.

2. *Privacy risk:*

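### Demographics and yes/no symptoms are to be compared by chi-square or Fisher tests with no effect estimate or interval; baseline tests are uninformative, and a non-significant symptom result could not by itself support a tolerability statement

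*Combined protocol and SAP*

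**What the plan says.** The Statistical Analysis part of Section 8 has three elements: a non-parametric test for the primary outcome, a description of the pain course in the whole cohort, and the sentence "Chi square analysis and fisher exact tests will be used to compare demographics and dichotomous variables as appropriate". That sentence is the only between-arm plan beyond the primary outcome. It mentions no risk difference, ratio or confidence interval, and no other section supplies one.

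The baseline items are in Section 7, step 2: "Relevant baseline demographics (age, race, ethnicity, education level, gravidity, detailed parity", followed by histories of anxiety, depression, drug abuse and chronic pain, recent narcotic use and the reason for termination. That makes 12 items, all collected before the study drug is taken.

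Sedation and dizziness are recorded at baseline and five minutes after insertion (Section 7, steps 3 and 6), by text at 2, 4 and 8 hours (step 9), and on pre-operative admission (step 10). Step 9 records them as present or absent, and the text questions can be answered yes or no. Section 8 does not name them. That they belong to the dichotomous variables is an inference, though a natural one.

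**The concern.** Allocation is computer-generated by the pharmacist, stratified and blinded. For variables fixed before allocation, the null hypothesis of a baseline test is true by design. A significant result can only be a chance finding, yet it may be read as a fault in the randomisation.

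For sedation and dizziness the null may well be false, and the question is how large any excess is. These are the two side effects that Section 12 says the trial will monitor, and the ride-home requirement in Section 4 exists because of possible sedation. The sample size calculation concerns pain only. If a test result is all that is reported, p>0.05 could reflect no excess or a moderate excess that was missed, and the reader cannot tell which.

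**Working it through.** **Inputs from the protocol**

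- Total size: "we will more than double the sample size to recruit 121 women". This was chosen rather than derived: 48 x 1.2 = 57.6, rounded to 58, and 121/58 = 2.09. The protocol states no power or sample size for side effects, so there is no figure of its own to reproduce on this point.
- Allocation ratio: not given as a number. Section 7, step 4a, says only "This strategy will ensure similar numbers of women with vaginal parity between gabapentin and placebo groups". Assuming 1:1, 121/2 gives about 60 per arm.
- Non-response: up to 20% for the primary outcome. 121 x 0.8 = 96.8, about 48 per arm answering texts.
- Significance level: 0.05 in the pain calculation. Two-sided 0.05 is assumed here for the other comparisons.
- Symptom rates: not given. All rates below are assumptions.

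**Baseline tests**

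The chance of at least one p<0.05 among k independent tests under valid randomisation is 1 - 0.95^k.

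- k = 12 (all items in step 2): 1 - 0.95^12 = 0.460
- k = 11 (leaving out parity): 1 - 0.95^11 = 0.431

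These are closer to upper figures than to expected ones. Several items are plausibly correlated (anxiety with depression, race with ethnicity), Fisher's test usually rejects less often than its nominal level in small samples, and age and gravidity would need grouping before either test applied.

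**Power for a symptom excess**

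With rates p1 and p2, mean rate m = (p1 + p2)/2 and n per arm:

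power = Phi[(|p2 - p1| - 1.96 x sqrt(2m(1 - m)/n)) / sqrt((p1(1 - p1) + p2(1 - p2))/n)]

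For 20% v 35% at n = 60, m = 0.275. The two square roots are 0.0815 and 0.0804, so power = Phi[(0.15 - 0.1598)/0.0804] = Phi(-0.12) = 0.45.

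| Assumed rates | 60 per arm | Fisher, exact (60 v 61) | 48 per arm | Fisher, exact (48 v 48) |
|---|---|---|---|---|
| 10% v 20% | 33% | 26% | 28% | 18% |
| 20% v 35% | 45% | 40% | 37-38% | 30% |
| 5% v 20% | 70% | 65% | 61% | 48% |
| 20% v 40% | 67% | 63% | 57% | 49% |

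For placebo rates from 5% to 50%, the excess detectable with 80% power is about 17 to 25 percentage points at 60 per arm and 20 to 28 points at 48 per arm.

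**What an interval would show**

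The simple (Wald) 95% half-width is 1.96 x sqrt((p1(1 - p1) + p2(1 - p2))/n).

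- 20% v 35%, n = 60: 1.96 x 0.0804 = 0.158, about 16 points
- 20% v 35%, n = 48: 1.96 x 0.0899 = 0.176, about 18 points
- 20% v 30%, n = 60: 1.96 x sqrt((0.16 + 0.21)/60) = 0.154

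In the last case the observed excess is 10 points, with an interval from about -5 to +25. The test would be non-significant, while the interval would show that an excess above 20 points had not been ruled out.

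**The case against.** The strongest reply is that this is a matter of reporting style. The sentence names tests but does not exclude proportions or intervals, and Section 12 promises close monitoring of side-effect frequency. That is fair: the supportable criticism is that estimation is not specified, not that the plan forbids it.

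It can also be said that the power figures depend on assumed rates and that larger excesses would usually be found. This stands too. At 60 per arm, power for a 20-point excess is about 59% to 88% over placebo rates of 5% to 50%, and excesses of about 25 points or more would usually be detected. The 48-per-arm case applies to the text assessments; symptoms recorded in clinic and before the procedure are not subject to the text non-response allowance.

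Four stronger readings are tempting and are not supported:

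- Section 12 observes that earlier gynaecologic studies "report no statistically significant increase in sedation or dizziness compared to placebo". A reader might infer that this trial will treat its own results the same way. That passage is background on participant risk, not an interpretation rule, and it also notes that studies of this kind were powered for pain.
- A reader might infer that covariates will be chosen from baseline p-values. The plan contains no adjusted model, so there is no route for this.
- A reader might count any use of as-needed analgesics among the planned dichotomous outcomes. The texts collect numbers of pills, and no yes/no version is defined.
- A reader might say that stratification makes any test of parity empty. The blocks balance only none versus one or more vaginal deliveries, not the detailed parity listed in step 2.

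**Conclusion.** The point holds as a modest improvement to reporting. Between-arm tests of demographics are uninformative in this design and could raise a false alarm in up to about 43% to 46% of sound trials if the tests were independent. Dropping them changes no trial result.

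The more useful part concerns sedation and dizziness. At about 60 per arm, moderate excesses would be missed about as often as found, or more often, over much of the assumed range, so p>0.05 alone could not support a tolerability statement. This rests on a 1:1 ratio, two-sided 0.05, assumed symptom rates, and the inference that these symptoms fall under the dichotomous variables. The primary analysis is unaffected.

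**What to change.** Replace the sentence in Section 8 with text to this effect: baseline characteristics will be tabulated by arm without significance tests; sedation and dizziness will be reported at each scheduled assessment as counts and percentages by arm, with the risk difference and its 95% confidence interval (Newcombe or Miettinen-Nurminen); any statement on tolerability will be worded from the interval and not from p>0.05.

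The documents define no excess of sedation or dizziness that would matter clinically, so no threshold is attached here. If the investigators want to make a positive tolerability claim, they should state beforehand the excess that the upper limit must exclude. Otherwise the interval should be reported as it stands.

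The cost is one sentence. No new data, visits or participants are needed.
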